13.3 Risks to Others: N/A

13.4 Definition of Adverse Events (AE):

An adverse event is any untoward medical occurrence in a clinical study participant that is temporally associated with the use of a medicinal product, whether or not it is considered related to the medicinal product. An adverse event can be any unfavorable and unintended sign, including an abnormal laboratory finding, symptom or disease (new or exacerbated), temporally associated with the use of a medicinal product.

13.5 Definition of a Serious Adverse Event (SAE):

A serious adverse event is an AE that fulfills at least one of the following criteria:

- Results in death

MEDICAL PROTOCOL (HRP-590)

PROTOCOL TITLE: Pharmacokinetics and Pharmacodynamics of Topiramate for Weight Loss in Youth: PHARMATOP

VERSION DATE: 05/03/2024

- Is life-threatening
- Requires inpatient hospitalization or prolongation of existing hospitalization
- Results in persistent disability/incapacity
- Is a congenital anomaly/birth defect

13.6 Classification of an Adverse Event:

Severity of Event: The severity of all AEs will be assessed by the internal safety monitor using the following grading system:

- *Grade 1: Mild:* asymptomatic or mild symptoms; clinical or diagnostic observations only; intervention not indicated
- *Grade 2: Moderate:* minimal, local or noninvasive intervention indicated; limiting age-appropriate instrumental activities of daily living
- *Grade 3: Severe:* medically significant but not immediately life-threatening; hospitalization or prolongation of hospitalization indicated; disabling; limiting self-care activities of daily life
- *Grade 4: Life-threatening:* urgent intervention indicated
- *Grade 5: Death:* related to adverse event

Relationship to Study Intervention: All AEs must have their relationship to study intervention assessed by the clinician who examines and evaluates the participant based on temporal relationship and his/her clinical judgment. The degree of certainty about causality will be graded using the categories below. In a clinical study, the study product must always be suspected.

- *Unrelated:* clearly not related to the investigational agent(s)
- *Unlikely:* doubtfully related to the investigational agent(s)
- *Possible:* may be related to the investigational agent(s)
- *Probable:* likely related to the investigational agent(s)
- *Definite:* clearly related to the investigational agent(s)

Expectedness: The internal safety monitor will be responsible for determining whether an AE is expected or unexpected. An AE will be considered unexpected if the nature, severity, or frequency of the event is not consistent with the risk information previously described for the study intervention.

13.7 Time Period and Frequency for Event Assessment and Follow-Up:

All AEs will be captured on the appropriate case report form (CRF). Information to be collected includes event description, time of onset, clinician's assessment of severity, relationship to topiramate (assessed only by those with the training and authority to make a diagnosis), and time of resolution/stabilization of the event. All AEs occurring while in the study must be documented appropriately regardless of relationship. All AEs will be followed to adequate resolution.

Any medical condition that is present at the time that the participant is screened will be considered as baseline and not reported as an AE. However, if the study participant's condition deteriorates at any time during the study, it will be recorded as an AE.

The study staff will record all reportable events with start dates occurring any time after informed consent is obtained until the last day of study participation. As described in **Section**

MEDICAL PROTOCOL (HRP-590)

PROTOCOL TITLE: Pharmacokinetics and Pharmacodynamics of Topiramate for Weight Loss in Youth: PHARMATOP

VERSION DATE: 05/03/2024

5.1. at each study encounter study staff will inquire about the occurrence of AEs/SAEs since the last encounter. Events will be followed for outcome information until resolution or stabilization.

The PI will notify the IRB and external medical monitor ([name]) of any SAE that meets the definition of being an unanticipated problem that involves risk to subjects or others (UPIRTSO) within five days of knowledge of the event. The DSMB will be provided with AE and SAE information prior to their review of the study, at least every six months.

14.0 Potential Benefits to Participants

14.1 Potential Benefits:

We believe the potential benefits to the participants outweigh the risks in this study. We expect that most, if not all, participants will experience some degree of weight loss and improvements in eating behaviors during the study. Since data from studies in youth receiving topiramate have shown an overall reduction in BMI with topiramate plus LSM, it is reasonable to expect similar results in this proposed study focused on characterizing associations between topiramate dose, exposure, and weight loss outcomes in youth with severe obesity.

15.0 Statistical Considerations

15.1 Data Analysis Plan:

PopPK analysis will be conducted using NONMEN® following best practice guidelines set forth by Byon et al.⁵⁶ We will assume that the structural model of topiramate follows a one-compartment model with 1st-order absorption and elimination per previous topiramate studies.²³⁻²⁵ Topiramate concentrations (collected 4, 6, 8, and 12 weeks after 75 mg or maximum-tolerated topiramate dose reached) will be modeled using non-linear mixed effects (NLME). Topiramate exposure (assessed by area under the curve (AUC)), as well as additional variables including apparent clearance, volume of distribution, and inter-individual variability will be estimated with popPK, described in **Section 15.3**. The effects association of topiramate exposure (AUC) on weight loss outcomes (BMI reduction, changes in eating behaviors and cardiometabolic risk labs) will be performed using linear regression with robust estimation for confidence intervals and p-values. We will also explore potential non-linear relationships with cubic splines.

15.2 Power Analysis:

In line with the goals of this pilot study, our sample size was chosen to strike a balance between recruitment, feasibility, potential attrition, and the amount of data deemed necessary to inform the aims and design of a subsequent NIH R01. Results from previous simulations and statistical methods for repeated measures outcomes using sparse sampling in popPK suggest that bias and precision are acceptable as sample sizes approach 50.⁵⁷⁻⁵⁹ Assuming 25% drop-out, higher than usual for CPOM clinical trials (10-15%), we will recruit 65 participants. The power will depend on the range of values observed for the exposure predictor (AUC). Based on the variability observed from a pilot study of similar dose and age, and allowing for drop-out of as many as 15, we will have 80% power for an association of 4.75kg per 20 mcg*h/ml.⁶⁰

15.3 Statistical Analysis:

Pharmacokinetic Modeling (dose-exposure relationships):

Topiramate concentrations will be modeled using a non-linear mixed effects (NLME) regression

MEDICAL PROTOCOL (HRP-590)

PROTOCOL TITLE: Pharmacokinetics and Pharmacodynamics of Topiramate for Weight Loss in Youth: PHARMATOP

VERSION DATE: 05/03/2024

implemented in NONMEM® (ICON Development Solutions, [name]). NLME is robust with respect to sparse data sets such as ours, hence appropriate for this analysis. Compartment models best describing topiramate will be selected based on diagnostic plots and fall in objective function values (OFVs). Covariates known to effect drug disposition (e.g. BMI, sex, race/ethnicity, genomics, as determined by a genetic risk score (GRS) will be included in the model-building algorithms. An automated stepwise covariate model (SCM) procedure will be used to screen covariates.³¹ The SCM involves forward selection and backward elimination steps: forward addition followed by backward deletion. Covariates that upon inclusion reduced the OFV by at least 3.84 (statistical significance of $p<0.05$, based on a Chi-squared distribution (degrees of freedom (df) = 1)), will be sequentially added. After stepwise addition of all significant covariates, backward deletion will be performed wherein removal of covariates that increase the OFV by at least 6.84 (statistical significance of $p<0.01$ based on a Chi-squared distribution (df = 1)), will be considered significant. Final model parameter estimates and their 95% confidence intervals will be qualified by re-estimation using a nonparametric bootstrap approach generating 1,000 bootstrap datasets. Parameter estimates are rank ordered and the values at the 2.5% and 97.5% of the rank order are used as the lower and upper bounds of the bootstrap 95% confidence interval. The 50th percentile (median) is used as the bootstrap parameter estimate.³¹

Pharmacodynamic Modeling (exposure-response relationships):

The association of topiramate exposure (AUC) on weight loss outcomes (BMI reduction, changes in eating behaviors and cardiometabolic risk labs) will be performed using linear regression, adjusting for model covariates, with robust estimation for confidence intervals and p-values. We will also explore potential non-linear relationships utilizing cubic splines.

15.4 Data Integrity:

Despite our best efforts, it is possible that some data will be missing, which could limit interpretation of the results. If the data are missing at random, conditioned on measured covariates, then supplementary analyses adjusting for these covariates will produce unbiased results. For potential missing data mechanisms beyond measured covariates, we will examine the extent to which results may be affected. Imputation techniques will be considered for missing data issues (e.g., multiple imputation). In particular, we will use a last observation carried forward approach for participants on whom we do not have a final measurement. Observations obtained during interim visits will be used for these analyses, and additional sensitivity analyses.

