3. *To determine associations between topiramate exposure and changes in cardiometabolic risk factor labs.* We hypothesize that higher topiramate exposure will be associated with greater 3-month improvements in insulin sensitivity (measured by homeostatic model assessment – insulin resistance (HOMA-IR) and hemoglobin A1c) and lipid levels (including increased HDL and lower LDL and triglycerides) in youth with severe obesity.
4. *To determine associations between body fat percentage and topiramate exposure, and to determine if body fat percentage is a better predictor of topiramate exposure compared to BMI.* We hypothesize that increased percent body fat (%BF) as assessed by dual x-ray absorptiometry (iDXA) and bioelectrical impedance (BIA) will be associated with decreased topiramate exposure, and that %BF will correlate more strongly with topiramate exposure compared to BMI in youth severe obesity.

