4.3 Biosafety: N/A

4.4 Stem Cells: N/A

4.5 Fetal Tissue: N/A

5.0 Procedures Involved

5.1 Study Design:

This will be a 3.5-month open-label, pragmatic-based study to determine associations between topiramate dose, exposure, weight loss outcomes (i.e., BMI reduction, improvements in cardiometabolic risk factor labs), and eating behaviors (i.e., hunger, satiety, binge eating, food craving, consumption of sugar-sweetened and/or carbonated beverages) in youth with severe obesity prescribed this medication for weight management. The study cohort will be recruited primarily among youth receiving care through our PWMCs. Additional study participants may be recruited among those who contact CPOM (after receiving recruitment letters for CPOM studies), are interested in participating in a study that specifically involves the initiation of an active anti-obesity pharmacotherapy at study onset (versus possibility of receiving a placebo), and who qualify (meet inclusion/exclusion criteria). We will recruit youth ages 12 to <18 years old. The schedule of events (**Table 1**) shows the data that will be collected at each study visit. Following topiramate initiation, adherence will be assessed every other week by review of electronic prescription bottles, and side effects will be assessed throughout the study at in-person study visits or via phone calls.

MEDICAL PROTOCOL (HRP-590)

PROTOCOL TITLE: Pharmacokinetics and Pharmacodynamics of Topiramate for Weight Loss in Youth: PHARMATOP
VERSION DATE: 05/03/2024

Table 1: Schedule of Events

	Screening/Baseline	Week 6	Week 8	Week 10	Week 14
Visit Number	1	2	3	4	5
Review Inclusion/Exclusion Criteria ¹	x				
Consent/Accent	x				
Demographics ²	x				
Physical Exam ³	x				x
Tanner Staging ³	x				
BMI/Anthropometrics ⁴	x	x		x	x
Blood Pressure/Heart Rate	x	x		x	x
Pregnancy Testing and questionnaire ¹⁴	x	x		x	x ¹⁴
Safety Labs ⁵	x	x			
Cardiometabolic Risk Labs (fasting) ⁶	x				x
Genotyping ⁷	x				
Topiramate concentration		x	x	x	x
iDXA (body composition) ⁸	x				
Bioelectrical Impedance Analysis ⁹	x	x		x	x
Eating Behavior and Physical Activity Questionnaires ¹⁰					
• Hunger/Satiety Visual Analog Scales					
• AEBQ					
• FCQ-T-r	x	x			x
• dYFAS					
• RED-5					
• PAQ-A					
Sugar Consumption ¹¹	x	x			x
• BEVQ-15					
Eating Disorder Examination Questionnaire (EDE-Q)	x	x			x
Depression and Suicide Screening ¹²	x	x	x	x	x
• PHQ-9					
• C-SSRS					
Neurocognitive Testing ¹³	x	x		x	x
• COWA					

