- Current or recent (< 6 months prior to enrollment) use of long-acting stimulant medications, **unless** participant has been on stable doses of such medication for \geq 6 months. In terms of short-acting ADHD stimulant medications, the PI will determine eligibility based on weight and dose (no studies have shown this contributes to weight outcomes).
- Baseline bicarbonate $<$ 18 mmol/L
- Baseline creatinine $>$ 1.2 mg/dL
- Females: pregnant, planning to become pregnant, or, if sexually active, unwilling to use 2+ acceptable contraceptive methods during the study period

8.3 Screening:

Patients seen in the University of Minnesota PWMCs who are deemed appropriate candidates to receive topiramate (without contraindications) for weight loss by an obesity medicine specialist will be referred for this study.

Screening/Baseline Visit (Visit 1):

Participants will be asked to present at this visit after having fasted for \geq 12 hours. At this visit, the participant's parent/legal guardian will be taken through the consent process and will sign the parental consent form, and the participant will be asked to sign the assent form, after all have had the opportunity to learn about the study and ask any questions they may have. The participant will then undergo the following:

- Review of inclusion/exclusion criteria
- Demographics including age, sex, self-reported race/ethnicity, home address, total family combined income, parents' level of education and employment status
- Physical exam and tanner stage. The physical examination will not need to be repeated if performed by a CPOM faculty member, pediatric weight management provider, and/or pediatric endocrinologist within the last 30 days before Screening/Baseline visit. A trained professional can perform the Tanner staging.
- BMI/Anthropometrics: height, weight, waist and hip circumference, and BMI
- Blood pressure and heart rate
- Pregnancy test for females
- Contraceptive counseling
- Review of medications
- Blood draw for safety labs (creatinine and bicarbonate) and cardiometabolic risk labs (lipids, glucose, insulin, and A1c)
- Genotyping (via saliva collection)
- iDXA (body composition)
- Bioelectrical impedance analysis (via Tanita Scale)
- Eating behavior and physical activity questionnaires (hunger/satiety visual analog scales, AEBQ, FCQ-T-r, dYFAS, RED-5, BEVQ-15, PAQ-A)
- Safety questionnaire for eating disorders (EDE-Q)

MEDICAL PROTOCOL (HRP-590)

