PROTOCOL TITLE: Pharmacokinetics and Pharmacodynamics of Topiramate for Weight Loss in Youth: PHARMATOP

VERSION DATE: 05/03/2024

- Depression and suicide screening (PHQ-9 and C-SSRS). Participants whose tests show that they have active suicidal ideation will be referred to their own mental health provider, have a mental health referral generated or be referred to the emergency department
- Neurocognitive testing (COWA test, NIH-TB List Sorting Working Memory Test, NIH-TB Pattern Comparison Processing Speed Test)
- Lifestyle and registered dietitian counseling

Week 2 (± 7 days from enrollment):

- Side effects, inter-current illnesses, medication review and adherence (via phone call)

Week 4 (± 7 days from enrollment):

- Side effects, inter-current illnesses, medication review and adherence (via phone call)

Week 6 (± 7 days from enrollment; Visit 2):

- BMI/Anthropometrics
- Blood pressure and heart rate
- Blood draw for safety labs (creatinine and bicarbonate)
- Pregnancy test for females
- Topiramate concentration
- Bioelectrical impedance analysis (via Tanita Scale)
- Eating behavior and physical activity questionnaires (hunger/satiety visual analog scales, AEBQ, FCQ-T-r, dYFAS, RED-5, BEVQ-15, PAQ-A)
- Safety questionnaire for eating disorders (EDE-Q)
- Depression and suicide screening (PHQ-9 and C-SSRS)
- Neurocognitive testing (COWA test, NIH-TB List Sorting Working Memory Test and NIH-TB Pattern Comparison Processing Speed Test)
- Lifestyle and registered dietitian counseling
- Side effects, inter-current illnesses, medication review
- Adherence (via electronic prescription bottle review and counting pills)

Week 8 (± 7 days from enrollment; Visit 3; lab draw only):

- Topiramate concentration
- Side effects, inter-current illnesses, medication review (via phone call or in-person)
- Adherence (via electronic prescription bottle review and counting pills)
- Suicide screening (C-SSRS)
- Drug dispensing

Week 10 (± 7 days from enrollment; Visit 4):

- BMI/Anthropometrics
- Blood pressure and heart rate

MEDICAL PROTOCOL (HRP-590)

PROTOCOL TITLE: Pharmacokinetics and Pharmacodynamics of Topiramate for Weight Loss in Youth: PHARMATOP

VERSION DATE: 05/03/2024

- Pregnancy test for females
- Topiramate concentration
- Bioelectrical impedance analysis (via Tanita Scale)
- Depression and suicide screening (PHQ-9 and C-SSRS)
- Neurocognitive testing (COWA test, NIH-TB List Sorting Working Memory Test, NIH-TB Pattern Comparison Processing Speed Test)

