- Side effects, inter-current illnesses, medication review
- Adherence (via electronic prescription bottle review and counting pills)

Week 14 (± 7 days from enrollment; Visit 5):

- Physical exam, performed by a trained pediatrician
- BMI/Anthropometrics
- Blood pressure and heart rate
- Blood draw for cardiometabolic risk labs (lipids, glucose, insulin, and A1c)
- Pregnancy test for females and questionnaire about the testing
- Topiramate concentration
- Bioelectrical impedance analysis (via Tanita Scale)
- Safety questionnaire for eating disorders (EDE-Q)
- Eating behavior and physical activity questionnaires (hunger/satiety visual analog scales, AEBQ, FCQ-T-r, dYFAS, RED-5, BEVQ-15, PAQ-A)
- Neurocognitive testing (COWA test, NIH-TB List Sorting Working Memory Test, NIH-TB Pattern Comparison Processing Test)
- Side effects, inter-current illnesses, medication review
- Suicide screening (C-SSRS)
- Adherence (via electronic prescription bottle review and counting pills)

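### Cardiometabolic labs have no interim value, so the carry-forward rule in Section 15.4 either scores a leaver's change as zero or has nothing to carry

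*Combined protocol and SAP*

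**What the plan says.** Section 3.2, objective 3, hypothesises that "higher topiramate exposure will be associated with greater 3-month improvements in insulin sensitivity" and in lipids. Sections 15.1 and 15.3 put the cardiometabolic labs into the same linear regression on AUC, with robust inference, that is used for BMI.

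Table 1 and the visit lists in Section 8.3 agree on when these labs are drawn:

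- **Screening/Baseline:** safety labs plus lipids, glucose, insulin and A1c.
- **Week 6:** the list gives "Blood draw for safety labs (creatinine and bicarbonate") and a topiramate concentration, but no cardiometabolic labs.
- **Weeks 8 and 10:** a topiramate concentration, and no cardiometabolic labs.
- **Week 14:** "Blood draw for cardiometabolic risk labs (lipids, glucose, insulin, and A1c"). This is the only on-treatment value.

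Sections 12.2 and 12.3 collect no data after withdrawal, and there is no early-termination draw.

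Section 15.4 says multiple imputation may be considered, then commits itself: "we will use a last observation carried forward approach for participants on whom we do not have a final measurement". The next sentence adds: "Observations obtained during interim visits will be used for these analyses". Neither sentence names an endpoint or makes an exception.

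On attrition, Section 15.2 states: "Assuming 25% drop-out, higher than usual for CPOM clinical trials (10-15%), we will recruit 65 participants".

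**The concern.** Carry-forward needs an on-treatment observation to carry. BMI has Weeks 6 and 10, and the eating questionnaires have Week 6. The labs have nothing between Baseline and Week 14, so the last observation for a leaver is the pre-treatment value, and the change is baseline minus baseline, which is zero whatever the exposure.

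Topiramate concentrations start at Week 6. Someone who leaves between Week 6 and Week 14 therefore has a measured exposure paired with an invented null response. A completer whose Week 14 sample is missed or unusable is in the same position. What is at stake is the exposure slope for objective 3, in a pilot that is meant to inform a later grant application.

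**Working it through.** **The plan's own sample size.** Section 15.2 wants about 50 evaluable participants and allows 25% drop-out. 50/(1 - 0.25) = 66.7, or 67. Multiplying instead, 50 x 1.25 = 62.5, or 63. The stated 65 lies between them and is reproduced within 2. The power statement's allowance of 15 leaves 65 - 15 = 50 (15/65 = 23.1%). A full 25% is 65 x 0.25 = 16.25, leaving 48.75, or about 49.

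**How many would be zero-scored.** Assume leaving times are uniform over 14 weeks (the documents do not say). Then (14 - 6)/14 = 8/14 of leavers go after Week 6, with an AUC but no final labs. Earlier leavers have no measured concentration and are left out of the regression.

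| Drop-out | Leavers | After Week 6 | Completers | Fraction zero-scored |
|---|---|---|---|---|
| 10% | 6.5 | 3.7 | 58.5 | 3.7/62.2 = 6% |
| 15% | 9.75 | 5.6 | 55.25 | 5.6/60.8 = 9% |
| 25% | 16.25 | 9.3 | 48.75 | 9.3/58.0 = 16% |
| 25%, all after Week 6 | 16.25 | 16.25 | 48.75 | 16.25/65 = 25% |

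The last row also applies if the population PK model supplies a covariate-predicted AUC for early leavers and they are kept in.

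**Effect on the slope, drop-out unrelated to AUC.** If a fraction f of records has response zero regardless of AUC, the expected slope is (1 - f) times the true slope. The documents give no slope for any lab, so a standardised value of -0.41 is assumed. This is close to the 0.396 implied by 80% power at n = 50 with two-sided alpha 0.05 (also assumed): (1.960 + 0.842)/sqrt(50) = 0.396. That power statement is in kg, so it is only a rough guide. Whole-number cases:

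- 56 completers, 5 zeros: -0.41 x 56/61 = -0.376
- 49 completers, 9 zeros: -0.41 x 49/58 = -0.346
- 49 completers, 16 zeros: -0.41 x 49/65 = -0.309

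Simulation (normal AUC and residuals, HC3 intervals, mean change 0 to 1 residual SD) agrees with these slopes. Coverage of the true slope is about 94%, 91-93% and 85-88% respectively. Observed Week 14 values alone give -0.41 with about 95%.

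**Why coverage falls.** With 49 completers, 9 zeros and mean change 0, the mean HC3 standard error is 0.131 and the empirical SD of the slope is about 0.127. With 16 zeros they are 0.119 and 0.116. The standard error is right for the estimator; the interval is centred on a shrunken slope.

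**True slope zero.** With drop-out still unrelated to AUC, the rejection rate stays at about 5%.

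**Drop-out related to AUC.** Illustration with N = 65, all with an AUC, standardised slope 0.396 and mean change of 1 residual SD:

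| Who leaves more often | 7 zeros | 15 zeros |
|---|---|---|
| High AUC | 0.45 of true slope | 0.12 |
| Low AUC | 1.11 | 1.21 |

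Observed-only analysis stayed within 1% of the true slope in all four cells. The sizes depend on the assumed mean change; the point is that the bias can take either sign.

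**The case against.** **Section 15.4 never says that baseline is carried, nor that change is zero.** This stands. A reader might infer that the plan prescribes zero-scoring. It is the literal result of the rule when baseline is the only earlier value, not stated text. The sentence that follows points to interim visits as the source; on that reading nothing is carried and objective 3 has no committed method. Both readings need the same correction.

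**Section 15.4 offers more than carry-forward.** It also mentions covariate-adjusted supplementary analyses, an examination of other missingness mechanisms, multiple imputation and sensitivity analyses. True, but imputation is only to be considered and none of these is specified for the labs. Carry-forward is the only approach it commits to.

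**A reader might infer that constant zeros make the standard error too small.** The simulation does not support this: the robust standard error matches the estimator's spread, and coverage is lost through attenuation. Nor does the plan support a claim about a diluted mean improvement, because the labs are to be analysed by regression on AUC.

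**The size rests on pessimistic and borrowed inputs.** Largely true. The plan calls 25% higher than its usual 10-15%, and Section 25.1 reports 85-90% retention in longer trials. At that level 4 to 6 participants are affected and the effect is small. With an assumed slope of -0.2, coverage is about 94% with 9 zeros and 92-93% with 16. The power loss ranges from about 1 to 11 points with the assumed mean change and number of zeros, so no single figure should be quoted.

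**Conclusion.** The point holds as a minor correction to a secondary objective. The schedule and the carry-forward rule do not fit together for HOMA-IR, HbA1c and lipids: the rule either enters a zero change or supplies nothing, and the plan does not say which.

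Under literal use, with drop-out unrelated to AUC, attenuation is about 6-9% at the usual drop-out, about 16% at the planned 25%, and at most about 25%. The first two figures assume uniform leaving times; the coverage figures assume a slope of -0.41. In that setting the error is conservative and creates no false positives. That reassurance goes if leaving depends on AUC, which the documents neither assert nor rule out.

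The point does not extend to the primary BMI outcome in this form, because BMI has on-treatment values at Weeks 6 and 10.

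**What to change.** Add to Section 15.4:

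> Cardiometabolic labs have no interim measurement; baseline values will not be carried forward. Objective 3 will be analysed in participants with an observed Week 14 value, with multiple imputation (baseline labs, AUC, age, sex, interim BMI change) as a sensitivity analysis. The number of participants with an AUC but no Week 14 labs will be reported.

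The cost is a few sentences and one small additional analysis, with no new visits or assays. The stated sample for objective 3 becomes smaller, about 49-50 at the planned drop-out, but it is the number that actually carries information on the outcome. Observed-only analysis gives an unbiased slope when leaving depends on AUC or on covariates in the model. It does not protect against leaving that depends on the unseen lab change itself; the imputation analysis helps only as far as baseline labs and interim BMI change predict that change.
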